5.5. Method of Assessing Treatment Compliance

DS-8201a will be administered IV only to subjects participating in the study and under the supervision of clinical study personnel at the site. Start and stop times of injection and amount of drug administered are to be recorded by clinical study personnel.

5.6. Concomitant Medications, Treatments, And Procedures

Medications used from the time the subject signs the informed consent form to 40 days (+ 7 days) after the last administration of DS-8201a will be recorded. All concomitant medications will be recorded on the CRF.

The following medications, treatment and procedures will be prohibited during the treatment period (see Section 4.2 for required washout periods):

- Other anticancer therapy, including cytotoxic, targeted agents, immunotherapy, antibody, retinoid, or anti-cancer hormonal treatment.
- Other investigational therapeutic agents.
- Radiotherapy (except for palliative radiation to known metastatic sites as long as it does not affect assessment of response or interrupt treatment for more than the maximum time specified in dose modification section).
- Radiotherapy to the thorax.
- Concomitant use of chronic systemic (IV or oral) corticosteroids or other immunosuppressive medications. (Inhaled steroids or intra articular steroid injections are permitted in this study.)
 - Subjects with bronchopulmonary disorders who require intermittent use of bronchodilators (such as albuterol) will not be excluded from this study.
- CYP3A4 strong inhibitors (eg, boceprevir, clarithromycin, conivaptan, indinavir, itraconazole, ketoconazole, lopinavir/ritonavir, mibefradil, nefazodone, saquinavir, telaprevir, telithromycin, voriconazole). Please consult with your local resources as needed to evaluate potential CYP3A4 inhibitors (see Section 17.5 for more extensive list).

If concomitant use of strong CYP3A4 inhibitors is unavoidable, consider delaying DS-8201a treatment until the strong CYP3A4 inhibitors have cleared from the circulation (approximately 3 elimination half-lives of the inhibitors) when possible. If a strong CYP3A4 inhibitor is co-administered and DS-8201a treatment cannot be delayed, subjects should be closely monitored for adverse reactions.

- Organic anion transporting polypeptide (OATP)1B inhibitors including but are not limited to: atazanavir, clarithromycin, cyclosporine, erythromycin, gemfibrozil, lopinavir, rifampin, ritonavir, simeprevir. Consult with your local resources as needed to evaluate potential OATP1B inhibitors (see Section 17.5 for more extensive list).
- If concomitant use of OATP1B inhibitors is unavoidable, consider delaying DS-8201a treatment until the OATP1B inhibitors have cleared from the circulation (approximately $3 \times$ the elimination half-life of the inhibitors) as long as possible.
- If an OATP1B inhibitor is co-administered and DS-8201a treatment cannot be delayed, subjects should be closely monitored for adverse reactions.
- Foods or beverages containing grapefruit;

Hematopoietic growth factors may be used for prophylaxis or treatment based on the clinical judgment of the investigator.

Prophylactic or supportive treatment of study-drug induced AEs will be otherwise as per investigator's discretion and institutional guidelines.

Concomitant use of dietary supplements, medications not prescribed by the investigator, and alternative/complementary treatments is discouraged, but not prohibited.

5.7. Removal of Subjects From Treatment and/or Study

5.7.1. Reasons for Discontinuation of Study Treatment

Subjects may be withdrawn from study treatment after signing informed consent for the following reasons:

- Progressive disease per criteria set forth in RECIST version 1.1;
- Clinical progression (definitive clinical signs of (PD), but a recent radiographic assessment did not meet the criteria for Progressive Disease according to RECIST version 1.1);
- Adverse event;
- Withdrawal of consent by subject;
- Physician Decision;
- Death;
- Pregnancy;
- Study terminated by Sponsor;
- Lost to follow-up;
- Other, specify.

If there is evidence that the subject is receiving benefit from treatment even though the subject has met a criterion for discontinuation as listed above, the subject may remain on study treatment after discussion with the Global Clinical Lead.

All subjects who are withdrawn from study treatment should complete protocol-specified withdrawal procedures (Section 5.7.3) and follow-up procedures (Section 6.6).

Record the reason for any subject who discontinues study treatment. Discontinued subjects will be followed for survival, either through direct contacts or by collecting public records (eg, death certificates) as allowed by local laws.

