5.4. Dose Interruptions and Reductions

The investigator will evaluate which toxicities are attributed to the study drug and adjust the dose of the drug as recommended below. All dose modifications should be based on the worst preceding toxicity (common toxicology criteria [CTC]AE version 4.03). Specific criteria for interruption, re-initiation, dose reduction and/or discontinuation of DS-8201a are listed in [Table 5.2](#). All interruptions or modifications must be recorded on the AE and drug administration case report form (CRF). Appropriate clinical experts should be consulted as deemed necessary.

For Grade 3 or Grade 4 events, monitoring (including local laboratory tests when appropriate) should be performed at intervals no greater than 7 days until AE is determined to be resolving or subject is discontinued at end of treatment.

Prophylactic or supportive treatment for expected toxicities, including management of study-drug induced AEs will be as per treating physician discretion and institutional guidelines.

Dose Reduction Guidelines:

NOTE: There will be no dose modifications for Grade 1 or Grade 2 AEs unless specified below in [Table 5.2](#).

Two dose reductions will be permitted. The adjustment for reduced dosing of DS-8201a is as shown in [Table 5.1](#).

Table 5.1: Dose Reduction Levels of DS-8201a

Starting Dose	Dose Level -1	Dose Level -2
7.4 mg/kg	6.4 mg/kg	5.4 mg/kg
6.4 mg/kg	5.4 mg/kg	4.4 mg/kg
5.4 mg/kg	4.4 mg/kg	3.2 mg/kg

Once the dose of DS-8201a has been reduced because of toxicity, all subsequent cycles should be administered at that lower dose level unless further dose reduction is required. More than 2 dose reductions are not allowed and the subject will be withdrawn from the study treatment if further toxicity meeting the requirement for dose reduction occurs. DS-8201a dose increases are not allowed in the study.

Dose can be interrupted for up to 28 days from the planned date of administration. If a subject is assessed as requiring a dose delay longer than 28 days, the subject will be withdrawn from the study.

Treatment cycles for a subject for whom DS-8201a dosing was temporarily withheld for any reason may have future cycles scheduled based on the date of the last DS-8201a dose.

Investigators may contact the Sponsor’s Global Clinical Lead or designee to discuss questions regarding dose modification or discontinuation of study drug.

Table 5.2: Dose modification for DS-8201a

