Worst toxicity CTCAE v4.03 Grade (unless otherwise specified)	Dose or schedule modification for DS-8201a
No toxicity	Maintain dose and schedule
Infusion Reaction	
Grade 1 (Mild transient reaction; infusion interruption not indicated; intervention not indicated)	If infusion-related reaction (such as fever and chills, with and without nausea/vomiting, pain, headache, dizziness, dyspnea, hypotension) is observed during administration, the infusion rate should be reduced by 50% and subjects should be closely monitored. If no other reactions appear, the subsequent infusion rate could be resumed at the initial planned rate.
Grade 2 (Therapy or infusion interruption indicated but responds promptly to symptomatic treatment (eg, antihistamines, nonsteroidal anti-inflammatory drugs (NSAIDs), narcotics, IV fluids); prophylactic medications indicated for ≤24 h)	Administration of DS-8201a should be interrupted and symptomatic treatment started (eg, antihistamines, NSAIDs, narcotics, intravenous fluids). If the event resolves or improves to grade 1, infusion can be re-started at a 50% reduced infusion rate. Subsequent administrations should be conducted at the reduced rate.
Grade 3 or 4 (Prolonged or life-threatening consequences, urgent intervention indicated)	Administration of DS-8201a should be discontinued immediately and permanently. Urgent intervention indicated. Antihistamines, steroids, epinephrine, bronchodilators, vasopressors, intravenous fluid therapy, oxygen inhalation etc., should be administered.

Table 5.2: Dose modification for DS-8201a (Continued)

Worst toxicity CTCAE v4.03 Grade (unless otherwise specified)	Dose or schedule modification for DS-8201a
Hematologic Toxicity	
Neutrophil Count Decreased and/or White Blood Cell Count Decreased	
Grade 3	Delay dose until resolved to \leq Grade 2, then maintain dose
Grade 4	Delay dose until resolved to \leq Grade 2, Reduce dose 1 level
Febrile Neutropenia (absolute neutrophil count $< 1 \times 10^9/L$, fever $> 38.3^\circ C$ or a sustained temperature of $\geq 38^\circ C$ for more than one hour)	Delay dose until resolved, Reduce dose by 1 level
Lymphocyte Count Decreased	
Grade 1 to Grade 3 lymphopenia	No dose modification
Grade 4 ($< 0.2 \times 10^9/L$)	Delay dose until resolved to \leq Grade 2: 
 • If resolved in ≤ 14 days, maintain dose • If resolved in > 14 days, reduce dose 1 level
Anemia	

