Grade 3 (Hemoglobin (Hg) < 8.0 g/dL); transfusion indicated	Transfuse. Delay dose until resolved to \leq Grade 2, then maintain dose
Grade 4 (Hg < 8.0 g/dL) Life threatening consequences; urgent intervention indicated	Transfuse. Delay dose until resolved to \leq Grade 2, then reduce dose 1 level
Platelet Count Decreased	
Grade 3 (platelets < 50 to $25 \times 10^9/L$)	Delay dose until resolved to \leq Grade 1: 
 • If resolved in ≤ 7 days, maintain dose • If resolved in > 7 days, reduce dose 1 level
Grade 4 (platelets $< 25 \times 10^9/L$)	Delay dose until resolved to \leq Grade 1, then reduce dose 1 level
Cardiac Toxicity	
Symptomatic congestive heart failure (CHF)	Discontinue subject from study treatment
Decrease in left ventricular ejection fraction (LVEF) 10-20% (absolute value), but LVEF $> 45\%$	Continue treatment with DS-8201a
LVEF 40% to $\leq 45\%$ and decrease is $< 10\%$ (absolute value) from baseline	Continue treatment with DS-8201a Repeat LVEF assessment within 3 weeks

Table 5.2: Dose modification for DS-8201a (Continued)

Worst toxicity CTCAE v4.03 Grade (unless otherwise specified)	Dose or schedule modification for DS-8201a
LVEF 40% to \leq 45% and decrease is \geq 10% (absolute value) from baseline	Interrupt DS-8201a dosing Repeat LVEF assessment within 3 weeks. If LVEF has not recovered to within 10% from baseline, discontinue subject from study treatment
LVEF < 40% or > 20% (absolute value) drop from baseline	Interrupt DS-8201a dosing Repeat LVEF assessment within 3 weeks. If LVEF < 40% or > 20% drop from baseline is confirmed, discontinue subject from study treatment
Corrected QT (QTc) Prolongation	
Grade 3 (QTc > 500 ms on 2 separate electrocardiograms)	Delay dose until resolved to \leq Grade 1 (QTc \leq 480 ms), determine if another medication the subject was taking may be responsible and can be adjusted, then if attributed to DS-8201a, reduce dose 1 level
Grade 4 (QTc > 500 or > 60 ms change from baseline and Torsade de pointes or polymorphic ventricular tachycardia or signs/symptoms of serious arrhythmia)	Discontinue subject from study treatment
Troponin	

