Pulmonary Toxicity	
If a subject develops an acute onset of new or worsening pulmonary or other related signs/symptoms such as dyspnea, cough or fever, rule out ILD/pneumonitis.
 
If the AE is confirmed to have an etiology other than ILD/pneumonitis, follow the management guidance outlined in the “Other Non-Laboratory Adverse Events” dose modification section below.
 
If the AE is suspected to be ILD/pneumonitis, treatment with study drug should be interrupted pending further evaluations.
 
Evaluations should include:
 
 • High resolution CT • Pulmonologist consultation • Pulmonary function tests and pulse oximetry (SpO₂) • Arterial blood gases if clinically indicated • One blood sample collection for PK and exploratory biomarker analysis as soon as ILD/pneumonitis is suspected, if feasible 
Other tests could be considered as needed.
 
As soon as ILD/pneumonitis is suspected, corticosteroid treatment should be started promptly as per clinical treatment guidelines (Kubo K, et al 2013 for guidance²²).
 
If the AE is confirmed to be ILD/pneumonitis, follow the management guidance as outlined below.
 
All events of ILD regardless of severity or seriousness will be followed until resolution including after drug discontinuation.

Grade 1	
The administration of DS-8201a must be interrupted for any ILD event regardless of grade.
 
For Grade 1 events, DS-8201a can be restarted only if the event is fully resolved to Grade 0:
 
 • If resolved in ≤ 28 days from day of onset, maintain dose • If resolved in > 28 days from day of onset, reduce dose 1 level
Grade 2, 3, or 4	Permanently discontinue subject from study treatment.
Ocular	
Grade 3	
Delay dose until resolved to \leq Grade 1:
 
 • If resolved in ≤ 7 days, maintain dose • If resolved in > 7 days, reduce dose 1 level
Grade 4	Discontinue subject from study treatment
Renal Toxicity (serum creatinine)	
Grade 3 (> 3 to $6 \times$ upper limit of normal [ULN])	Delay dose until resolved to \leq Grade 2 or baseline, then reduce dose 1 level
Grade 4 ($> 6 \times$ ULN)	Discontinue subject from study treatment

Table 5.2: Dose modification for DS-8201a (Continued)

Worst toxicity CTCAE v4.03 Grade (unless otherwise specified)	Dose or schedule modification for DS-8201a
Hepatic Toxicity	

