Aspartate Transaminase (AST) or Alanine Transaminase (ALT) with Simultaneous Total Bilirubin (TBL) Increased	
AST/ALT $\geq 3.0 \times$ ULN with simultaneous TBL $> 2.0 \times$ ULN	
Delay study medication until drug-induced liver injury can be ruled out. If drug-induced liver injury is ruled out, the subject should be treated accordingly, and resumption of study drug may occur after discussion between the investigator and Sponsor.
 
If drug-induced liver injury cannot be ruled out from diagnostic workup, permanently discontinue study treatment.
 
Monitor AST/ALT and TBL twice weekly until resolution or return to baseline.

Aspartate Transaminase (AST) or Alanine Transaminase (ALT)	
Grade 2 ($> 3.0 - 5.0 \times$ ULN)	No action for Grade 2 AST/ALT
Grade 3: $> 5.0 - 20.0 \times$ ULN In subjects without liver metastases and subjects with liver metastases and baseline level $\leq 3 \times$ ULN:	
Repeat testing within 3 days. Delay dose until resolved to \leq Grade 1, then:
 
 • If resolved in ≤ 7 days from day of onset, maintain dose • If resolved in > 7 days from day of onset, reduce dose 1 level
Grade 3 ($> 8.0 - 20.0 \times$ ULN) In subjects with liver metastases, if the baseline level was $> 3 \times$ ULN	
Repeat testing within 3 days. Delay dose until resolved to \leq baseline level, then:
 
 • If resolved in ≤ 7 days from day of onset, maintain dose • If resolved in > 7 days from day of onset, reduce dose 1 level
Grade 4 ($> 20 \times$ ULN)	Discontinue subject from study treatment
Total Bilirubin	
Grade 2 ($> 1.5 - 3.0 \times$ ULN)	
If no documented Gilbert's syndrome or liver metastases at baseline, delay dose until resolved to \leq Grade 1:
 
 • If resolved in ≤ 7 days from day of onset, maintain dose • If resolved in > 7 days from day of onset, reduce dose 1 level 
If documented Gilbert's syndrome or liver metastases at baseline, continue study treatment

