Grade 3 ($> 3.0 - 10.0 \times$ ULN)	
If no documented Gilbert's syndrome or liver metastases at baseline, repeat testing within 3 days. Delay dose until resolved to \leq Grade 1:
 
 • If resolved in ≤ 7 days from day of onset, reduce dose 1 level • If resolved in > 7 days from day of onset, discontinue DS-8201a 
If documented Gilbert's syndrome or liver metastases at baseline, repeat testing within 3 days. Delay dose until resolved to \leq Grade 2:
 
 • If resolved in ≤ 7 days from day of onset, reduce dose 1 level • If resolved in > 7 days from day of onset, discontinue DS-8201a
Grade 4 ($> 10.0 \times$ ULN)	Discontinue subject from study treatment
Alkaline Phosphatase Increased	
Grade 3 or 4 ($> 5.0 \times$ ULN)	No modification unless determined by the investigator to be clinically significant or life-threatening

Table 5.2: Dose modification for DS-8201a (Continued)

Worst toxicity CTCAE v4.03 Grade (unless otherwise specified)	Dose or schedule modification for DS-8201a
Gastrointestinal	
Nausea	
Grade 3	Delay dose until resolved to \leq Grade 1: 
 • If resolved in \leq 7 days, maintain dose • If resolved in $>$ 7 days, reduce dose 1 level
Diarrhea/Colitis	
Grade 3	Delay dose until resolved to \leq Grade 1: 
 • If resolved in \leq 3 days, maintain dose • If resolved in $>$ 3 days, reduce dose 1 level
Grade 4	Discontinue subject from study treatment
Other Laboratory Adverse Events	
Grade 3	Delay dose until resolved to \leq Grade 1 or baseline level: 
 • If resolved in \leq 7 days, maintain dose • If resolved in $>$ 7 days, reduce dose 1 level
Grade 4	Discontinue subject from study treatment
Other Non-laboratory Adverse Events	
Grade 3	Delay dose until resolved to \leq Grade 1 or baseline: 
 • If resolved in \leq 7 days, maintain dose • If resolved in $>$ 7 days, reduce dose 1 level
Grade 4	Discontinue subject from study treatment

All dose modifications should be based on the worst preceding toxicity.

CTCAE: Common Terminology Criteria for Adverse Events.

In addition, investigators may consider dose reductions or discontinuations of the study drug according to the subject's condition and after discussion with the Sponsor Global Clinical Lead or designee.

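### The continuation sentence in Section 5.7.1 is worded too broadly: it should be limited to progression and made subordinate to the toxicity stops in Table 5.2 and Section 5.4

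*Combined protocol and SAP*

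**What the plan says.** Section 5.7.1 of the protocol opens permissively: subjects may be taken off treatment for any of ten reasons. Two concern progression (RECIST 1.1 and clinical). The others are adverse event, withdrawal of consent, physician decision, death, pregnancy, sponsor termination, loss to follow-up and an open other category. The sentence at issue follows the list. It says that where a subject who appears to benefit "has met a criterion for discontinuation as listed above, the subject may remain on study treatment after discussion with the Global Clinical Lead". No list item is excluded.

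Section 5.4 deals with toxicity separately. It states that "Specific criteria for interruption, re-initiation, dose reduction and/or discontinuation of DS-8201a are listed in" Table 5.2. Several rows of that table are worded as stops:

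- Grade 3 or 4 infusion reaction: "Administration of DS-8201a should be discontinued immediately and permanently".
- Grade 2, 3 or 4 ILD/pneumonitis: "Permanently discontinue subject from study treatment".
- Raised transaminases with raised bilirubin: "If drug-induced liver injury cannot be ruled out from diagnostic workup, permanently discontinue study treatment".
- Symptomatic heart failure, and most Grade 4 non-haematologic toxicities: "Discontinue subject from study treatment".

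The text of Section 5.4 adds two stops. On dose reductions, "More than 2 dose reductions are not allowed and the subject will be withdrawn from the study treatment" if a further one is called for. A delay of more than 28 days also leads to withdrawal, and Section 3.1.1 repeats this as a delay of more than 4 weeks.

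**The concern.** For one event, such as Grade 2 pneumonitis in a responding subject, the protocol contains a rule that stops drug and a sentence that, on its face, allows drug to continue. A responder with a stop-level toxicity is the subject for whom an investigator would be most tempted to use the sentence. The stated conditions are evidence of benefit and a discussion with one sponsor role. Section 5.7.1 mentions no approval, documentation or renewed consent.

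The toxicity that matters most is ILD/pneumonitis. Section 9.3.1.1 calls it an important identified risk, and Section 1.3 reports two fatal cases adjudicated as ILD and as related to the drug. Section 9.3.1.1 also says that none had been reported in this study as of 13 Dec 2017, when few subjects had been dosed and treatment had been short.

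There is oversight. The study team reviews individual data continually and aggregate safety data monthly (Section 11.5.1), and an independent committee adjudicates potential ILD (Sections 9.3.1.3 and 9.12). Neither is stated to decide whether dosing continues, and there is no Data Monitoring Committee.

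**Working it through.** No formula applies, and the plan gives no figure to reproduce. The check is a comparison of texts in three steps.

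**Step 1. Scope of the permissive sentence.** It refers back to the whole list in Section 5.7.1. The adverse event item carries no qualifier, so on its wording the sentence reaches toxicity.

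**Step 2. Stops with no benefit exception.** Table 5.2 was read row by row.

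| Type of stop | Rows | Count |
|---|---|---|
| On the event or grade alone | Infusion reaction Grade 3/4; symptomatic heart failure; QTc Grade 4; ILD Grade 2–4; Grade 4 ocular, renal, AST/ALT, bilirubin, diarrhoea/colitis, other laboratory, other non-laboratory | 11 |
| After a further condition | LVEF 40–45% with a fall of at least 10% and no recovery on repeat; LVEF below 40%, or a fall above 20%, confirmed on repeat; troponin Grade 3 with infarction confirmed; AST/ALT with bilirubin and drug-induced liver injury not ruled out; bilirubin Grade 3 taking more than 7 days to resolve | 5 |

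11 + 5 = 16 rows. Three of them say that the stop is permanent: infusion reaction, ILD, and liver injury not ruled out. The haematologic rows contain no discontinuation rule. The third-reduction stop and the 28-day stop in Section 5.4 are additional to the 16.

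**Step 3. Is there a statement of which rule prevails?**

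- Section 3.1.1 makes continued treatment depend on the dosing criteria and on there being no unacceptable toxicity. It does not mention the Section 5.7.1 sentence.
- Section 3.1.3 lets dosing run until a Section 5.7.1 event occurs. It does not rank that section against Table 5.2.
- Section 5.4 places the specific discontinuation criteria in Table 5.2. It also introduces the dose adjustments as recommended, which someone favouring continuation could cite.
- The text after Table 5.2 says "investigators may consider dose reductions or discontinuations of the study drug". That discretion runs only towards less drug, but the text does not limit Section 5.7.1.
- The row for AST/ALT with bilirubin allows resumption after discussion with the sponsor, but only once drug-induced liver injury is ruled out. So where the drafters wanted dosing to resume through discussion, they wrote it into the row.
- Section 9.3.1.2 sends confirmed ILD to the pulmonary rows and is silent on Section 5.7.1.
- Section 15.5 bars deviations and waivers. An investigator using Section 5.7.1 could answer that the protocol itself permits continuation, so there is no deviation.

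Most of these places point towards Table 5.2 governing. None states it.

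**Pregnancy.** Section 5.7.1 lists it among the reasons for which subjects may be withdrawn, so the continuation sentence reaches it literally. Section 9.7 asks only for notification, follow-up and outcome reporting. Section 3.1.3, through its reference to the Section 5.7.1 events, already treats pregnancy as ending dosing. The loose end is the wording of Section 5.7.1.

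**The case against.** The strongest reply is that there is no real conflict. The literal scope cannot be intended, because the list includes death, loss to follow-up and withdrawal of consent, after which continuation is impossible. The list reads as a set of reasons to record, and only its progression items have criteria that a subject can meet. The specific rule in Table 5.2 reads naturally over the general sentence. The adverse event item also has harmless work to do: it covers discretionary stops that Table 5.2 does not order.

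Most of this stands as evidence of intent, and a careful investigator would probably follow the table. What does not follow is that the text settles the matter. Each step is an inference, and about 110 sites would each have to make it for a safety stop.

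A reader might infer something stronger: that Section 5.7.1 overrides the toxicity stops, or that the protocol authorises re-dosing after Grade 2–4 ILD. The documents do not support that. The sentence does not name Table 5.2, and the surrounding text leans the other way. Nor should the stops be called mandatory without qualification, given that Section 5.4 describes the dose adjustments as recommended, although the stop rows themselves are worded as instructions. A reader might also infer that nothing ends dosing on pregnancy; Section 3.1.3 shows otherwise.

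**Conclusion.** The point holds as a drafting fault with a safety consequence. The continuation sentence is broader than its probable purpose, and no section states that the toxicity stops prevail. It should be corrected at the next amendment.

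Its textual extent is 16 rows of Table 5.2, three of them expressly permanent, plus two stops in Section 5.4. That count measures how far the overlap reaches, not how often harm would follow. The documents give no basis for a number of affected subjects, and none is offered. The sentence does not enter the sample size calculation in Section 11.6 or the primary ORR analysis in Section 11.4.1.1.

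The conclusion rests on reading the reference to the list in Section 5.7.1 as covering every item. That is the plain wording, though probably not what was meant.

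**What to change.** Replace the continuation sentence in Section 5.7.1 with text such as:

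> A subject who is still benefiting despite RECIST 1.1 progression or clinical progression may continue study drug once the case has been discussed with the Global Clinical Lead. This provision never applies where Table 5.2 or Section 5.4 requires discontinuation, or to pregnancy.

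This keeps treatment beyond progression, the likely purpose of the sentence, and brings the pregnancy wording into line with Section 3.1.3. The cost is two sentences at the next amendment. The downside is slightly less discretion to continue dosing after toxicity in a responding subject.
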